Clinical Study Protocol

Project Title:

Predictive Value of Serum Histone Succinylation in Malignant Solid Tumors

Leading institutions:

The First Affiliated Hospital of Xinxiang Medical University

School of Life Sciences, East China Normal University

Version: V4.1

Date: 19-Jul-2025

Principal Investigators: [name], [name]

Protocol Approval:

2025
7/19

Compliance Statement

Participants must comply with the Declaration of Helsinki and commit to conducting this study in accordance with this protocol. They must be trained and the study can only be carried out after obtaining written approval from the ethics committee and written informed consent from the subjects. Any revision to the protocol requires re-approval.

一、 scenario summary

In recent years, with the in-depth research on post-translational modifications of proteins, scientists have discovered that histone succinylation modification, as a novel protein modification method, is closely related to the occurrence, development and prognosis of tumors. Succinylation modification affects processes such as cell metabolism, proliferation and apoptosis by altering the physicochemical properties and functions of proteins. In tumor cells, the abnormal expression of succinylation modification is closely related to tumor type, stage and prognosis, providing new ideas for the early diagnosis of tumors. This project uses blood serum samples and detects and analyzes the level of histone succinylation modification in the serum through specific histone succinylation modification antibodies. Combined with other clinical information, it aims to achieve early, rapid and accurate diagnosis of pan-tumors, realize the rapid screening of tumors with "one tube of blood", and promote the transformation of precise early diagnosis of tumors from "gene-driven" to "epigenetic metabolism-driven". The implementation of this project aims to explore the feasibility of histone succinylation modification in serum as a tumor marker, providing more effective biomarkers for tumor early screening, therapeutic effect evaluation and prognosis. This will help develop more accurate and convenient blood testing methods in the future, benefiting a wider patient population and having significant social value.

二、 introduction

2.1 Research background, project objectives and the foundation of previous research

2.1.1 Research background

Cancer has become a major social, economic and public health issue in the 21st century and is one of the leading causes of death worldwide. In 2020, both the number of new cancer cases and deaths in China ranked first in the world. With the rapid development of medical technology, early diagnosis of tumors is of vital importance for improving the survival rate and quality of life of patients. However, existing tumor diagnostic methods, such as imaging examinations, histopathological examinations, and traditional tumor marker detection, still have deficiencies in terms of sensitivity,

specificity, and early detection capabilities. They cannot achieve the detection of multiple tumors with a single method, and may have limitations such as high professional requirements, long time consumption, and high detection costs. Therefore, it is of vital importance to develop a novel pan-tumor screening and diagnosis method that is low-cost, highly sensitive and highly specific.

Free nucleosomes in cells are nucleosomes released into circulating tissues after apoptosis or necrosis of cells, and they retain some specific information of the origin cells and tissues. The histone modification status on the free nucleosomes produced by tumor cells reflects the metabolic state and epigenetic changes of tumor cells. Therefore, histone modification of free nucleosomes in cells is expected to become a new biomarker for non-invasive tumor detection. Although previous studies have found the association between histone succinylation modification and tumors, and free nucleosomes in cells retain specific histone modifications of the origin tumor cells, histone succinylation modification of free nucleosomes in cells has not yet been applied to tumor screening and detection. Therefore, it is urgently necessary to study whether histone succinylation modification of free nucleosomes can be used as a low-cost, highly sensitive and highly specific pan-tumor marker and applied in the early screening, therapeutic effect evaluation and prognosis of tumors.

Succinylation modification, as a widely existing post-translational modification of proteins, has potential biomarker value in malignant solid tumors. Besides tumors, existing studies have shown that some diseases (such as inflammatory diseases, infectious diseases, metabolic diseases, cardiovascular diseases, neuro-psychological diseases, etc.) have certain correlations with non-histone succinylation modification. The role of histone succinylation modification in other diseases is currently lacking in relevant clinical research evidence and awaits further exploration in this study. Therefore, this research focuses on malignant solid tumors, not only filling the knowledge gap in this field but also laying the foundation for future expansion to other diseases.

2.1.2 project objective

The core objective of the project is to systematically verify and establish the clinical

application value of serum histone succinylation modification as a novel, efficient and non-invasive pan-tumor biomarker.

Objective 1: Verify the potential of pan-tumor screening: Through large-scale case-control studies, it is clearly confirmed that there are significant differences in histone succinylation levels in serum between patients with malignant solid tumors and healthy individuals, thereby providing a solid evidence-based basis for developing it into a blood-based early screening tool suitable for multiple tumor types.

Objective 2: Exploring clinical application scenarios: The project will conduct an in-depth analysis of the association between serum histone succinylation levels and different types of tumors as well as different tumor stages, and evaluate its ability to distinguish tumor types and reflect disease progression. Meanwhile, analyze its correlation with therapeutic effects (changes in levels before and after surgery, radiotherapy, and systemic treatment) and clinicopathological characteristics, and explore its application prospects in dynamic monitoring of therapeutic effects and prognosis assessment.

2.1.3 Preliminary research foundation

(1) [name] research group from East China Normal University previously discovered that histone succinylation modification was significantly higher in various solid tumors than in adjacent tissues. The results are shown in the following figure: Histone succinylation modification at the H4K31 site was significantly higher in various solid tumors than in adjacent tissues.

[name] research group previously prepared histones from human breast cancer, prostate cancer, lung cancer, kidney cancer, and lung cancer tissue samples from mice. The Western blot results (see Figure 1) indicated that the levels of succinylation modifications at histone H4K31 and H3K14 sites in cancer tissues were significantly higher than those in adjacent tissues, such as breast cancer (Figure 1A), prostate cancer (Figure 1B), renal cancer (Figure 1C), and lung cancer (Figures 1D and 1E). It reveals that histone succinylation modification can serve as a potential biomarker for tumorigenesis and development.

[figure not shown]

Figure 1: The succinylation modification at the histone H4K31 site in tumor tissues was significantly higher than that in adjacent tissues: (A) Western blot analysis of the levels of succinylation modification and histone acetylation modification at the histone H4K31 site in human breast tumor samples compared with those in adjacent tissues; (B) Western blot was used to analyze the levels of succinylation modification and histone acetylation modification at the histone H4K31 site in human prostate tumor samples compared with those in adjacent tissues. (C) Western blot was used to analyze the levels of succinylation modification and histone acetylation modification at the histone H4K1 site in human renal tumor samples compared with those in adjacent tissues. (D) Western blot was used to analyze the levels of succinylation modification and histone acetylation modification at the histone H4K31 site in human lung tumor samples compared with those in adjacent tissues.

Based on the findings in solid tumors, the level of histone succinylation modification in tumor tissues was significantly higher than that in adjacent tissues. Therefore, the research group, in collaboration with hospitals, collected blood samples from patients with different types of tumors and found that the succinylation modification at the H3K23 site of free nucleosome histones in the blood of tumor patients was significantly higher than that of normal people. However, the number of serum

samples from cancer patients still needs to be further expanded.

The research group previously isolated free nucleosomes from human colon cancer, gastric cancer, breast cancer, lung cancer, pancreatic cancer, multiple myeloma, liver cancer, cervical cancer, prostate cancer, ovarian cancer, esophageal cancer, cholangiocarcinoma and normal people's blood for Western blot. The results and gray-scale analysis statistics (see Figure 2) indicate that the succinylation modification of free nucleosome histone H3K23 sites in the blood of patients with different types of tumors (for specific information on different tumor types, see Figure 3) is significantly higher than that of normal people, revealing that the succinylation modification of free nucleosome histone in the blood of tumor patients may serve as a biomarker for the early diagnosis of tumors. However, at present, due to the small sample size, it is necessary to carry out this project to further expand the sample size and conduct in-depth research.

[figure not shown]

Figure 2 shows that the levels of free nucleosome histone succinylation modification in the blood of patients with different types of tumors are significantly higher than those of normal people: Enrich the free nucleosomes in the blood of tumor patients. Use histone H3K23 specific site succinylation modification and histone H3 acetylation modification antibodies to analyze the levels of histone succinylation modification and acetylation modification of free nucleosomes in the blood of different types of tumor patients by Western blot. And conduct gray-scale analysis and statistics on the Western blot results. Among them, N: normal human serum; T: Serum of cancer patients. Specific information on different types of tumors is shown in Figure 3.

Sample	Cancer patients	Sample	Controls
T1	Colon Cancer	N1	Healthy
T2	Stomach Cancer	N2	Healthy
T3	Colon Cancer	N3	Healthy
T4	Breast Cancer	N4	Healthy
T5	Breast Cancer	N5	Healthy
T6	Colon Cancer	N6	Healthy
T7	Colon Cancer	N7	Healthy
T8	Lung Cancer	N8	Healthy
T9	Lung Cancer	N9	Healthy
T10	Stomach Cancer	N10	Healthy
T11	Pancreatic Cancer	N11	Healthy
T12	Multiple myeloma	N12	Healthy
T13	Multiple myeloma	N13	Healthy
T14	Liver Cancer	N14	Healthy
T15	Cervical Cancer	N15	Healthy
T16	Lung Cancer	N16	Healthy
T17	Lung Cancer	N17	Healthy
T18	Prostate Cancer	N18	Healthy
T19	Ovarian Cancer	N19	Healthy
T20	Breast Cancer	N20	Healthy
T21	Ovarian Cancer	N21	Healthy
T22	Stomach Cancer	N22	Healthy
T23	Stomach Cancer	N23	Healthy
T24	Lung Cancer	N24	Healthy
T25	Stomach Cancer	N25	Healthy
T26	Stomach Cancer	N26	Healthy
T27	Stomach Cancer	N27	Healthy
T28	Pancreatic Cancer	N28	Healthy
T29	Pancreatic Cancer	N29	Healthy
T30	Pancreatic Cancer	N30	Healthy
T31	Pancreatic Cancer	N31	Healthy
T32	Esophageal Cancer	N32	Healthy
T33	Liver Cancer		
T34	Liver Cancer		
T35	Bile Duct Cancer		
T36	Bile Duct Cancer		
T37	Bile Duct Cancer		
T38	Ovarian Cancer		
T39	Ovarian Cancer		
T40	Cervical Cancer		

Figure 3. Information of different types of tumor samples and information of normal people

2.2 Risk/Benefit assessment

risk assessment:

This study was an observational one, and the core intervention was only a single venous blood sample collection of 3mL (approximately 1ml of serum). This operation

is a routine and mature medical practice in clinical practice, with extremely low and controllable risks.

Benefit evaluation:

Cancer patients: They will not receive immediate individualized diagnosis or treatment recommendations from this study. However, the data it contributes will drive the development of better tumor markers, which may benefit its future disease management (such as more precise follow-up monitoring).

Healthy control subjects: Contribute to establishing baseline standard values for healthy populations and promote public health. After the research is completed and the method is mature, the baseline data in which it participated may provide a reference background for its own future similar screening.

三、 Research objectives and endpoints

3.1 objective

3.1.1 main purpose

To evaluate the differences in serum histone succinylation between malignant solid tumors and healthy individuals, in order to verify its early screening value.

3.1.2 secondary objective

To clarify the correlation between histone succinylation modification in serum and different types of tumors and tumor stages, and to statistically analyze the correlation between histone succinylation in serum and therapeutic effects (including surgical treatment, radiotherapy, and systemic therapy) as well as clinicopathology.

3.2 evaluation index

The evaluation indicators are: the sensitivity, specificity, positive predictive value, negative predictive value of the serum histone succinylation screening method, and the predictive value of the Youden index (early diagnosis, therapeutic effect evaluation and prognosis).

四、 study population

4.1 inclusion criteria

case group

- 1) ≥ 18 years old, gender not limited;
- 2) Malignant solid tumors diagnosed by cytology or histology require subsequent anti-tumor treatment (systemic therapy, radical or concurrent chemoradiotherapy/radiotherapy, or surgical treatment).

control group

- 1) ≥ 18 years old, gender not limited;
- 2) Non-tumor patients undergoing health check-ups;

4.2 exclusion criteria

- 1) Pregnant women
- 2) Those with severe mental disorders or language communication disorders;
- 3) Other circumstances where the researcher deems it unsuitable to participate in this study.

The control group was the same as the case group.

五、 study design

5.1 overall design

This study is a single-center prospective case-control study.

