5.2.2 Research flowchart

5.2.3 Blood collection process table

grouping								
	Screening period							
healthy person	D-7—D0							
Cancer patients are receiving systemic treatment		Chemotherapy cycle						
		C1D1	C2	C3	C4	C5	C6	
	D-7—D0			D1± 3		D1±3		
Cancer patients who receive radical chemoradiotherapy/radiotherapy	D-7—D0	After the completion of radiotherapy/chemoradiotherapy		Four to six weeks after the completion of radiotherapy/chemoradiotherapy				
		D _{end} D _{end} +3		On the day of follow-up				
A tumor patient undergoing surgery	D-7—D0	postoperation	Postoperative discharge day/the day before discharge					
	D1—D3							

5.3 statistic analysis

This study adopted a mismatched case-control study (500 cases in the case group and 500 cases in the healthy control group). The sample size was determined based on the effect size of the previous pre-experiment (Cohen's $d=1.2$) and considering a 10% dropout rate. All statistical analyses were performed using R, with a test level of $\alpha=0.05$. Main analysis 1) Comparison of histone succinylation levels between groups - After Shapiro-Wilk normality and Levene homogeneity of variance tests, independent sample t-tests (conforming to normal distribution) or Mann-Whitney U tests (non-normal data) were selected. Report mean difference (MD)/median difference and 95% confidence interval (CI), Cohen's d effect size; 2) Diagnostic

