efficacy evaluation - Calculate the area under the curve (AUC) and its Bootstrap 95% CI through the ROC curve, and determine the optimal cut-off value by maximizing the Youden index. And calculate the sensitivity, specificity, positive predictive value (PPV), negative predictive value (NPV), and their exact Clopper-Pearson 95% CI. Secondary analysis: 1) Subgroup correlation - One-way analysis of variance (ANOVA) or Kruskal-Wallis test was used to compare the level differences among different tumor types (Bonferroni-adjusted post hoc test), and Cuzick's trend test was used to analyze the ordered association of TNM stages; 2) Therapeutic effect evaluation - The level changes before and after treatment were evaluated using paired t-test /Wilcoxon signed-rank test; 3) Prognostic value - The baseline succinylation level (median grouping) was included in the Cox proportional hazards model. After adjusting for age, stage, and treatment regimen, the hazard ratio (HR) and 95% confidence interval (CI) were calculated. The survival curve was plotted using the Kaplan-Meier method (Log-rank test). Multivariate analysis: A Logistic regression model was constructed (including succinylation level and covariates such as age and gender). AUC was compared by DeLong test, goodness-of-fit was evaluated by Hosmer-Lemeshow calibration curve, and clinical net benefit was analyzed by decision curve (DCA). If multi-site modifications are detected, LASSO regression is used to screen biomarker combinations. Quality control: Grubbs test /Winsorize for outliers, multiple imputation (MICE) for filling <5% of missing covariates. Sensitivity analysis: Robustness was verified by excluding stage I tumors, and the 70%-30% dataset was split for cutoff value training - validation. All multiple comparisons were controlled for the false discovery rate (FDR) using the Benjamini-Hochberg method.

六、Ethical requirements

Clinical research will comply with relevant regulations such as the Declaration of Helsinki of the World Medical Congress. The research can only be implemented after it has been approved by the ethics committee before it commences.

Before each subject is enrolled in this study, the researcher is responsible for providing the subject or their agent with a complete and comprehensive introduction

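### Section 3.2 asks for predictive value in prognosis and treatment effect, but 5.3 plans discrimination measures only for the case-control diagnostic analysis

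*Protocol*

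**What the plan says.** Section 3.2 (evaluation index) lists sensitivity, specificity and the two predictive values of the screening method, and then "the predictive value of the Youden index (early diagnosis, therapeutic effect evaluation and prognosis". Read literally, one measure is to serve three uses.

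Section 5.3 (statistic analysis) treats the three uses differently:

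- **Diagnosis (main analysis 2).** A ROC analysis is to "determine the optimal cut-off value by maximizing the Youden index", followed by sensitivity, specificity and predictive values with confidence intervals. This is the only place where 5.3 uses the Youden index.
- **Treatment effect (secondary analysis 2).** Only a before/after comparison is named: "The level changes before and after treatment were evaluated using paired t-test /Wilcoxon signed-rank test".
- **Prognosis (secondary analysis 3).** The marker enters a survival model as two groups: "Prognostic value - The baseline succinylation level (median grouping) was included in the Cox proportional hazards model". What is reported from that model is one hazard ratio with its interval, with age, stage and regimen as covariates. Curves and a test complete the analysis: "The survival curve was plotted using the Kaplan-Meier method (Log-rank test".

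Section 5.2.1 adds that treatment effect is assessed by RECIST 1.1. Section 5.3 does not say how that response enters the analysis.

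**The concern.** A hazard ratio states how far the event rates of two groups differ on average. A paired test states whether the mean or median level moved. Neither says how well the marker separates patients who will have an event, or who will respond, from those who will not. That separation is what sensitivity, specificity and the Youden index measure, and 3.2 asks for predictive value in all three uses.

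If 5.3 is followed as written, a statement that the marker has predictive value for prognosis would rest on a significant hazard ratio, and one for treatment effect on a significant before/after change. The paired test does not use response status at all. If levels fell equally in responders and non-responders, the test could be highly significant while the change carried no information about response (Youden index 0).

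**Working it through.** **Comparison of the sections.** The protocol gives no figure on this point to reproduce, so the check begins with the text.

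| Use named in 3.2 | Analysis in 5.3 | Discrimination measure planned? |
|---|---|---|
| Early diagnosis | ROC, AUC, Youden cut-off, sensitivity, specificity, predictive values | Yes |
| Treatment effect | Paired t-test or Wilcoxon signed-rank test | No |
| Prognosis | Adjusted Cox hazard ratio, Kaplan-Meier, log-rank | No |

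Two other items in 5.3 might fill the gaps, but neither does so as written. The first is the multivariate analysis: "A Logistic regression model was constructed (including succinylation level and covariates such as age and gender). AUC was compared by DeLong test". It is listed apart from the prognostic analysis, names no outcome, and is not linked to survival or response. The second is the 70%-30% split, which trains and validates a cut-off value. The only cut-off that 5.3 optimises is the diagnostic one, since prognosis uses the median.

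**How far a hazard ratio and the Youden index can diverge.** This is an illustration. The protocol states no hazard ratio, event share, survival endpoint or follow-up length, so the first two are assumed and varied.

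Inputs:

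- From 5.3: "500 cases in the case group and 500 cases in the healthy control group", so 500 patients enter the prognostic analysis; a median split, so half are in each group; α = 0.05, taken as two-sided.
- Assumed: proportional hazards; hazard ratio (HR) 1.5, 2 or 3; share of patients with an event by time t (e) 10% to 70%.

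Formulas, with S the survival at t in the low-risk half:

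- S solves 1 − 0.5 × (S + S^HR) = e.
- Sensitivity = 0.5 × (1 − S^HR) / e.
- Specificity = 0.5 × S / (1 − e).
- Youden index J = sensitivity + specificity − 1.
- Expected log-rank z = √(500e/4) × ln(HR).

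Worked case, HR 2.0 and e = 0.50:

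- S + S² = 1 gives S = 0.618 and S² = 0.382.
- Sensitivity = 0.5 × 0.618 / 0.5 = 0.618.
- Specificity = 0.5 × 0.618 / 0.5 = 0.618.
- J = 0.236.
- z = √62.5 × 0.693 = 5.48, so power exceeds 0.99.

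| HR | J at 10% events | 30% | 50% | 70% | Power at 50% events |
|---|---|---|---|---|---|
| 1.5 | 0.11 | 0.12 | 0.14 | 0.17 | 0.89 |
| 2.0 | 0.18 | 0.20 | 0.24 | 0.29 | >0.99 |
| 3.0 | 0.27 | 0.31 | 0.37 | 0.44 | >0.99 |

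Two results follow. A hazard ratio that this study would detect with high power can go with a low Youden index. And the hazard ratio does not fix the Youden index: at HR 2.0, J runs from 0.18 to 0.29 with the event share alone.

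**The case against.** The strongest reply is that 3.2 is garbled, probably in translation. The predictive value of a Youden index has no clear statistical meaning. The sentence may attach the Youden index to the screening method only and then, separately, name the marker's predictive value for the three uses. On that reading 5.3 follows the same order and contains no flat contradiction. This stands: a reader might infer that the protocol fixes the Youden index for prognosis and then drops it, but the wording is too loose to carry that. What remains is that predictive value is tied to prognosis and treatment effect on either reading.

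A reader might also infer that the planned survival analysis holds nothing about prediction. That goes too far. If the Kaplan-Meier curves are drawn by the median groups, as seems intended, the two survival values at a chosen time give sensitivity and specificity by the formulas above. What is missing is a named time point and an instruction to report them.

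Third, prognosis is marginal here. Section 3.1.1 concerns the case-control difference, 3.1.2 speaks of correlation and does not name prognosis, and 2.1.2 only proposes to explore it. An adjusted hazard ratio is a conventional answer to an exploratory question of association. This also stands and limits the weight of the point.

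Finally, time horizons and censoring methods are commonly left to a SAP, which is not shown. That is fair for the detail. It does not remove the mismatch between what 3.2 asks for and what 5.3 lists.

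**Conclusion.** The point holds in moderate form. Section 3.2 asks for predictive value in three uses, and 5.3 plans discrimination measures for one. For prognosis and treatment effect, the listed analyses would support statements of association or change, not of predictive value.

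The size can only be illustrated. With HR 2.0 and half the patients having an event, the Youden index is about 0.24; across HR 1.5 to 3 and event shares of 10% to 70%, it runs from 0.11 to 0.44. These values rest on assumed hazard ratios and event shares, proportional hazards and an even split. They show what could happen and do not forecast this study's result.

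The main case-control analysis is unaffected.

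**What to change.** **Prognosis (5.3, secondary analysis 3).** Keep the hazard ratio as the measure of association. Add the C-index of the Cox model with and without the marker, with age, stage and treatment regimen in both models, and a bootstrap 95% CI for the gain. Where follow-up allows, also report sensitivity, specificity and Youden index at one pre-specified time horizon, by a method that allows for censoring.

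**Treatment effect (5.3, secondary analysis 2).** Add sensitivity, specificity and Youden index of the level change against RECIST 1.1 response, in the patients who have a response assessment.

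**Claims.** Base any statement of predictive value in these two uses on the added measures.

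**Alternative.** If the additions are not wanted, limit the Youden index in 3.2 to the diagnostic analysis and describe the prognosis and treatment analyses as association only. That is a wording change.

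**Cost.** A few lines in 5.3 and a little more analysis. The C-index gain needs no data beyond those of the planned Cox model, and the response analysis uses assessments that 5.2.1 already foresees. The fixed-horizon measures are more demanding: they need a defined survival endpoint and enough follow-up to the horizon, and the protocol states neither. The prognostic result is likely to look less favourable than a hazard ratio with a small p-value.
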